Process Measures: To refine the intervention for future studies, participating clinicians will respond to questions about helpfulness, ease of use of the coaching intervention, the extent that they would recommend this training to a colleague.

Pilot: Prior to starting recruitment, we will do a small pilot test of the patient recruitment and data collection with up to 20 patients. The purpose is to ensure that the patients are able to use the tablet and the workflow is feasible within the clinic. We will follow the same patient recruitment plan and data collection process, including the inclusion/exclusion criteria. The patients will be patients who are attending their cardiology visit with the study co-investigator, [name] or with [name], a collaborator on the project. We will recruit additional cardiology patients with permission from their doctor. All of the patients' data, including survey responses and audio-recordings will be deleted within 60 days of collection. The only record of the patient's participation will be their signed consent form.

Selection of Subjects

In total, up to 720 people will consent to participate: 50 clinicians, up to 500 patients to complete the survey and audio-recording and another 150 patients to verbally consent to audio-recording the visit but no surveys. Up to 20 patients will consent to participate in the pilot.

Clinicians: Cardiologists who provide ambulatory cardiology care in a Duke cardiology clinic at least ½ day per week are eligible.

We will work with the Duke Division Chief of Cardiology to identify and recruit clinicians across Duke's ambulatory cardiology clinics.

Patients: Patients must be at 18 years or older, identify as Black/African-American or White, can read and speak English, not hospitalized, capable of providing informed consent and be a new or return patient of an enrolled clinician. Patients who are accompanied by a third-party member that is not willing or able to remain in the waiting room during the patient's visit and 1) does not wish to be recorded; 2) a minor without a parent/legal guardian; 3) unable to consent will be excluded. There are two types of patient participants: those who participate pre-intervention or post-intervention and those who participate during the intervention. Both types of patients must meet this eligibility criteria.

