General considerations: All variables will be described and explored using frequency tables, means, medians, standard deviations, histograms, box plots, and trajectory plots, both overall and within clinician. The primary analyses will be conducted on an intention-to-treat basis; clinicians and patients will be analyzed in the group to which they were randomized, regardless of clinician intervention adherence, using all available data. The main conclusions drawn from this trial will be based on the pre-specified hypotheses outlined below and will be tested with two-sided p-values at the standard 0.05 level. For all study outcomes, we will interpret differences between groups over time with reference to prior literature regarding clinically meaningful changes. Results from exploratory analyses will be interpreted with appropriate consideration for their exploratory nature. Statistical analyses will be performed using the latest release SAS for Windows (Cary, NC) and R/Rstudio.

The goal of the primary Hypothesis (1a) is to determine the efficacy of the clinician communication coaching intervention versus usual care on improvement in an objective measure of the quality of communication from baseline to post-training. Additionally, we are interested the intervention effect within Black patients and White patients separately. The quality of communication will be assessed at both baseline encounters and post-training encounters by a summary of clinician-encounter counts derived from the audio recordings. We plan to use mixed-effects models as our primary analytic strategy because they will appropriately account for the intracluster correlation of multiple patient encounters for each clinician and same clinicians followed over time. The mixed-effects model for Hypothesis 1a will have the following form: $\log(\mu_{ijk}) = \mu_0 + \mu_1(post) + \mu_2(post*int_k) + \mu_3(clinrace_k) + b_{0k} + b_{1kj}$, where Y_{ijk} is the number of quality communication statements for patient i at time j clustered within physician i , and Y_{ijk} is assumed to be Poisson with mean and variance equal to μ_{ijk} . The fixed effects in the model include indicator variables for the post-treatment ($post$), intervention group (int), and clinician race ($clinrace$). The random intercepts, b_{0k} and b_{1kj} , are normally distributed and account for dependence of encounters within clinicians, both between patients and on clinicians over time. PROC GLIMMIX (with

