### F.3 Aim 2 Analyses:

*Hypothesis 2a:* Racial disparities in objective measures of the quality of communication will be **lower** in encounters with clinicians in the intervention group as compared to encounters with clinicians in the control group.

*Hypothesis 2b:* Racial disparities in patients' perceptions of the quality of patient-centered care will be **lower** among those seen by clinicians in the intervention group as compared to encounters with clinicians in the control group.

A mixed-effects Poisson model will again be the primary modeling strategy for the objective communication outcome Aim 2 analyses. For this Aim, however, the model will include patientrace interaction terms and will have the following form:  $\log(\lambda_{ik}) = \lambda_0 + \lambda_1(\text{Black}_i) + \lambda_2(\text{int}_k) + \lambda_3(\text{Black}_i * \text{int}_k) + \lambda_4(\text{premean}_k) + \lambda_5(\text{clinsex}_k) + \lambda_6(\text{clintype}_k) + b_{0k}$ , where  $Y_{ijk}$  is the number of quality communication statements for patient  $i$  in the post-period clustered within physician  $k$ , and  $Y_{ik}$  is assumed to be Poisson with mean and variance equal to  $\lambda_{ik}$ . Again, the random intercept  $b_{0k}$  is normally distributed and account for dependence of encounters within clinicians. In this model,  $\text{Black}_i$  is the indicator variable for whether a patient is Black (value of 1) or White (value of 0).

Post-treatment, the Black-white mean difference among patients seen by usual care group clinicians is  $BW_{uc} = \exp(\lambda_0 + \lambda_1) - \exp(\lambda_0)$ , **this represents the racial disparity in communication quality**. The B-W mean difference among patients seen by intervention group clinicians is  $BW_{int} = \exp(\lambda_0 + \lambda_1 + \lambda_2 + \lambda_3) - \exp(\lambda_0 + \lambda_2)$ .

Hypothesis 2a will be tested by  $\lambda_5$  being significantly greater than zero, indicating a greater mean number of quality communication statements for the intervention group versus the control group for Black patients as compared to White patients (i.e., the intervention group reducing the racial disparity). The estimated incident rate ratio, p-value, and 95% confidence intervals will be calculated via estimate statements in PROC GLIMMIX.

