A similar linear mixed-effects model (rather than a Poisson) model will be used to examine the reduction in racial disparities of quality of patient-centered care and test Hypothesis 2b. Note that in a linear model framework, the coefficients will represent differences in means rather than rate ratios.

Power and Sample Size Considerations: The effect of interest for Aims 1 and 2 is the relative difference in the post-period between the intervention and usual care groups; Aim 1 focuses on the overall difference and the difference within Black and White patients separately, while Aim 2 on the difference within Black patients compared to White patients. The sample size requirements are greatest for Aim 2; as discussed by Leon and Heo (2009), the needed

sample size for the patient race-by-intervention group interaction is 4 times that needed for the overall test. For Hypotheses 1a and 2a, our sample size calculations are based upon the difference between two Poisson rates (incident rate ratio) in a cluster randomized design (i.e., patients clustered within clinician).

Based on preliminary studies, the baseline mean number of quality communication statements is 1.0, and a conservative range of coefficients of variation (CV) is 0.2 to 0.5 to account for patients clustered within clinician. With a **sample size of 240 patients in the post period (6 per clinician)** and a type-I error of 5%, we will have 80% power to detect incident rate ratios of 1.5 to 1.8 for Hypothesis 1a in the overall test, 1.6 to 1.9 for Black or White patients separately, and 1.8 to 2.5 for Hypothesis 2a.

For hypotheses 1b and 2b, our sample size calculations are based upon the difference between two means in a cluster randomized design. We present a conservative range of intraclass correlation coefficients (ICC) to account for patients clustered within clinician. With a **sample size of 240 patients (6 per clinician)** and a type-I error of 5%, we will have 80% power to detect mean differences of effect size 0.37 to 0.44 for Hypothesis 1b in the overall test, 0.52 to 0.56 for Black or White patients separately, and 0.65 to 0.91 for Hypothesis 2b. PASS 15 was used for all calculations.

	Number of clinicians	Number of patients in the postintervention phase (number per clinician)	Hypothesis 1a and 2a: Incident Rate Ratio		Hypothesis 1b and 2b: Mean Effect Size	
			CV	Pre-post Relative Rate	ICC	Pre-post Difference

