Aim 1: Overall intervention versus usual care	40 (20 in each treatment arm)	240 (6 per clinician)	0.2 0.35 0.5	1.5 1.6 1.8	0.01 0.05 0.1	0.37 0.41 0.44
Aim 1: Racial subgroup intervention versus usual care	40 (20 in each treatment arm)	120 (3 per clinician)	0.2 0.35 0.5	1.6 1.8 1.9	0.01 0.05 0.1	0.52 0.54 0.56
Aim 2: Racial differences in intervention versus usual care	40 (20 in each treatment arm)	Effective sample size is 60 (1 or 2 per clinician)	0.2 0.35 0.5	1.8-2.2 1.9-2.3 2.1-2.5	0.01 0.05 0.1	0.65-0.91 0.66-0.91 0.67-0.91

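### Hypothesis 2a: the race-by-arm standard error rests on variance = mean within clinician, an assumption the documents do not support with data; a negative binomial model would remove the dependence at little cost

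*SAP*

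**What the plan says.** SAP F.3 gives the 2a model as a log-linear mixed model for post-period counts. Its terms are Black, intervention, Black-by-intervention, the clinician's pre-period mean, clinician sex and clinician type. The count "is assumed to be Poisson with mean and variance equal to" the fitted mean. The single random effect, a clinician intercept, "is normally distributed and account for dependence of encounters within clinicians". The rate ratio, p-value and confidence interval come from estimate statements in PROC GLIMMIX.

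The protocol's Aim 2 model makes the same Poisson assumption. It adds a clinician-by-time intercept, which all of a clinician's patients in one period share.

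The protocol's General considerations say that hypotheses "will be tested with two-sided p-values at the standard 0.05 level". They also plan descriptive summaries, including "means, medians, standard deviations, histograms, box plots, and trajectory plots, both overall and within clinician". The available text has no rule that changes the 2a model or its standard error in response, and no dispersion parameter or robust standard error.

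The SAP power section states that "a conservative range of coefficients of variation (CV) is 0.2 to 0.5 to account for patients clustered within clinician", and gives a detectable ratio of "1.8 to 2.5 for Hypothesis 2a".

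(The SAP's test sentence for 2a names coefficient 5. In its own equation that is clinician sex, and Black-by-intervention is coefficient 3. This is a separate labelling matter; the interaction is meant throughout here.)

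**The concern.** A random intercept is often expected to absorb extra variation in counts. For a contrast made within clinicians it does not: it shifts a clinician's Black and White patients together, so it drops out of the difference between them. What remains is encounter-to-encounter variation within a clinician, and the model fixes that at the Poisson value instead of estimating it. The linear model for 2b, by contrast, estimates its residual variance.

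There are plausible sources of extra variation. For example, an eligible patient may "be a new or return patient of an enrolled clinician", and the model has no visit-type term. If encounters of one clinician vary more than Poisson, the 2a interval is too narrow and the test exceeds its nominal level. The protocol's Purpose section makes racial disparity in communication quality the primary outcome of Aim 2, so the practical risk is a false claim that coaching reduces it.

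**Working it through.** **Inputs.** From the SAP power section and table: 40 clinicians (20 per arm), 6 post-period patients each, 3 per race per clinician, mean count 1.0, between-clinician CV 0.2 to 0.5. From the protocol's General considerations: two-sided 0.05. Assumed: phi, the variance/mean ratio within clinician, because the documents give none.

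**1. The plan's own figure.** Use the cluster-randomised rate formula with c = 20 clinicians per arm, r0 = 1.0 and m patients per clinician:

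c = 1 + (1.960 + 0.842)² × [(r0 + r1)/m + CV²(r0² + r1²)] / (r0 − r1)²

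Solving for r1 with m = 2 and m = 1 gives 1.81–2.19, 1.92–2.30 and 2.09–2.47 at CV 0.2, 0.35 and 0.5. The SAP table gives 1.8–2.2, 1.9–2.3 and 2.1–2.5, so it reproduces. The (r0 + r1)/m term is the pure Poisson part; CV covers only variation between clinicians.

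**2. What the model's standard error contains.** With 3 Black and 3 White patients for every clinician, the fit reduces to the statement totals in the four race-by-arm cells:

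SE = sqrt(1/B_int + 1/W_int + 1/B_uc + 1/W_uc)

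Each cell expects 20 × 3 × 1.0 = 60 statements, so SE ≈ sqrt(4/60) = 0.258. A quadrature fit of a Poisson random-intercept model agreed with this formula to within 4e-8. Nothing in it responds to within-clinician spread. When the race mix is left to chance, the fitted SE is only 2 to 5% larger than the formula.

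**3. The actual error.** The true SD is about sqrt(phi) times the model SE, so the two-sided error is 2[1 − Φ(1.96/sqrt(phi))]. Simulated null trials used 3 + 3 patients per clinician, CV 0.35 and 100,000 trials per row:

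| phi | closed form | simulated, two-sided | simulated, favourable direction | median model SE | true SD |
|---|---|---|---|---|---|
| 1 | 5.0% | 5.0% | 2.5% | 0.260 | 0.262 |
| 1.25 | 8.0% | 7.8% | 3.9% | 0.261 | 0.293 |
| 1.5 | 11.0% | 10.8% | 5.5% | 0.261 | 0.322 |
| 2 | 16.6% | 16.4% | 8.2% | 0.262 | 0.373 |

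CV 0.2 and 0.5 agree within 0.2 points. With race mix left to chance (3,000 trials each), the two-sided errors are 5.5, 8.0, 10.9 and 16.1%.

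**4. An assumed scenario for phi.** Take an even mix of two visit types with overall mean 1.
- Rates 2-fold apart are 2/3 and 4/3. The variance of the rate is (1/3)² = 0.11, so phi ≈ 1.1. Simulated error: 6.4%.
- Rates 3-fold apart are 0.5 and 1.5. The variance of the rate is 0.5² = 0.25, so phi ≈ 1.25 (up to 1.28 once clinicians differ). Simulated error: 8.3%.

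**5. Detectable ratio.** ln R = 2.802 × sqrt(phi(3 + 1/R)/60) gives R = 1.97, 2.12, 2.27 and 2.56 at phi 1, 1.25, 1.5 and 2. Only the last lies above the SAP's upper figure of 2.5.

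**The case against.** The strongest reply is that the defect is hypothetical. No passage shows or implies overdispersion within clinician, and under the stated model the test is correct. At a mean of 1.0, phi = 1 + (encounter CV)², so ratios of 1.25, 1.5 and 2 need encounter CVs of 0.50, 0.71 and 1.00. The only CV in the documents, 0.2 to 0.5, describes a different quantity (clustering by clinician). Borrowed as a scale, it gives phi of 1.04 to 1.25 and errors of 5.5 to 8.0%. This stands, and it is why the size is put at about 6 to 8%, as an illustration.

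Three further limits also stand. The exact cancellation needs a 3/3 split in every clinician, whereas the protocol promises only about 50% Black patients overall; otherwise it is approximate. Both documents call 1a the primary hypothesis. The part of the SAP before F.2 was removed before review, so it could not be checked for a dispersion rule.

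What does not stand is the inference that no change is needed. The plan fixes the ratio at exactly 1 without data, and the planned descriptive summaries trigger no action.

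**Conclusion.** The 2a standard error depends essentially on variance = mean within clinician: exactly with 3 Black and 3 White patients per clinician, nearly so otherwise. The consequence is conditional. The error is about 5% if counts are Poisson given the clinician, and about 6 to 8% two-sided under the assumed visit mix.

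A reader might infer three stronger things that the documents do not support:
- That the 2a test will err at 11% or 16 to 17%. No scenario in the documents leads to a ratio of 1.5 or 2; those rows are a sensitivity range.
- That the CV of 0.2 to 0.5 is itself evidence of the problem. Alone it gives a marginal variance/mean of 1.04 to 1.25 (1 + CV²), which the random intercept handles.
- That the finding carries over to 1a. It does not: it concerns the within-clinician race contrast only.

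This is a worthwhile, inexpensive improvement, not a demonstrated error.

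**What to change.** Before unblinding, pre-specify one primary 2a analysis: a negative binomial conditional distribution in place of the Poisson (its limiting case), in the same GLIMMIX quadrature fit, with one stated reference distribution for the test. A t on 38 df (40 clinicians less 2 arms) is the choice that was checked. Over six scenarios (Poisson, the two visit mixes, and ratios 1.25, 1.5 and 2; 5,000 trials each) it gave errors of 3.6 to 4.9%, so it is slightly conservative. A clinician-level sandwich standard error with a named small-sample correction can be a sensitivity analysis only; otherwise one test has two possible standard errors. Do not choose the distribution from the data.

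The cost is a distribution option and a degrees-of-freedom statement, with no new data. If counts are Poisson, the SE is about 1% larger (0.264/0.2605 = 1.013). If t(38) is also chosen, the interval is about 5% wider (1.013 × 2.024/1.960 = 1.046). If counts are overdispersed, the SE is about 12%, 23% or 43% larger at ratios 1.25, 1.5 and 2 (0.293, 0.322 and 0.373 against about 0.261). That increase is real uncertainty; any further widening from a t reference is a separate choice.

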The cardiology encounter is a potentially high impact target for improved communication with a goal of reducing disparities for a number of reasons. First, compared to Whites, Blacks are 2 to 3 times more likely to die of cardiovascular disease. While the reason for these disparities are multifactorial, including differences in the social determinants, differences in the quality of care spanning stable low risk to lifethreatening cardiovascular issues contribute significantly to disparities. Blacks are less likely than whites to receive a range of cardiovascular treatments including angiograms, catheterizations, coronary bypass surgery, cardiac resynchronization therapy, automatic implantable cardioverter defibrillators, etc. Third, these disparities exist even when controlling for access to care, patient preferences, and appropriateness of therapies. Experiments using actors or clinical vignettes have indicated that providers are less likely to refer blacks than whites with same disease presentation for further evaluation or treatment and disparities are present even among those with similar insurance. This suggests that provider bias may contribute to disparities in communication and patient-centered care. Fourth, less than 1/3 of cardiology clinicians are aware of the existence of disparities. Awareness among clinicians is an important part of efforts to reduce and eliminate disparities. Fifth, cardiology encounters often involve recommendations to adhere to complex and life-long medication treatments; to undergo frightening, expensive procedures; and/or to make difficult lifestyle changes – all areas in which there are racial and ethnic disparities and in which effective communication is essential. Highly effective communication in the cardiology encounter may improve patient-centered care, leading to increased

adherence to cardiology treatments, acceptance of life-saving procedures, and implementation of effective preventive strategies.

Design & Procedures

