A mixed-effects Poisson model will again be the primary modeling strategy for the objective communication outcome Aim 2 analyses. For this Aim, however, the model will include patient-race interaction terms and will have the following form: $\log(\beta_{ijk}) = \beta_0 + \beta_1(Black_i) + \beta_2(T2) + \beta_3(T2*Black_i) + \beta_4(T2*int_k) + \beta_5(T2*Black_i*int_k) + \beta_6(race_k) + b_{0k}$ and b_{1kj} , where Y_{ijk} is the number of quality communication statements for patient i at time j clustered within physician k , and Y_{ijk} is assumed to be Poisson with mean and variance equal to β_{ijk} . Again, the random intercepts, b_{0k} and b_{1kj} , are normally distributed and account for dependence of encounters within clinicians, both between patients and on clinicians over time. In this model, $Black_i$ is the indicator variable for whether a patient is Black (value of 1) or White (value of 0).

Post-treatment, the Black-white mean difference among patients seen by usual care group clinicians is $BWuc = \exp(\beta_0 + \beta_1) - \exp(\beta_0)$, this represents the racial disparity in communication quality. The B-W

mean difference among patients seen by intervention group clinicians is $BW_{int} = \exp(\beta_0 + \beta_1 + \beta_2 + \beta_3) - \exp(\beta_0 + \beta_2)$.

Hypothesis 2a will be tested by β_5 being significantly greater than zero, indicating a greater improvement in the number of quality communication statements for the intervention group versus the control group for Black patients as compared to White patients (i.e., the intervention group reducing the racial disparity). The estimated incident rate ratio, p-value, and 95% confidence intervals will be calculated via estimate statements in PROC GLIMMIX.

A similar linear mixed-effects model (rather than a Poisson) model will be used to examine the reduction in racial disparities of quality of patient-centered care and test Hypothesis 2b. Note that in a linear model framework, the coefficients will represent differences in means rather than rate ratios.

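### The Hypothesis 2a model has no clinician random slope for patient race, so the race-by-arm standard error is too small if clinicians differ in their Black-White gap

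*SAP*

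**What the plan says.** SAP, F.3 Aim 2 Analyses: the 2a model for post-period counts has fixed effects for Black, arm, Black-by-arm, the clinician's pre-period mean, clinician sex and clinician type. Its single random term, the clinician intercept, "is normally distributed and account for dependence of encounters within clinicians". Counts are Poisson with variance equal to the mean.

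Protocol, F.3 Aim 2 Analyses: the longitudinal version has a clinician and a clinician-by-time intercept, which "are normally distributed and account for dependence of encounters within clinicians, both between patients and on clinicians over time". Neither involves race.

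For 2b the SAP writes no equation: "A similar linear mixed-effects model (rather than a Poisson) model will be used to examine the reduction in racial disparities". The random-effects structure of 2b is therefore inferred from the word 'similar'.

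Neither document gives a clinician-by-race term, a robust standard error, an overdispersion term or a degrees-of-freedom method. Under Data Analysis, the Protocol says the pre-specified hypotheses "will be tested with two-sided p-values at the standard 0.05 level".

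Below, the race-by-arm term is λ3 in the SAP equation and β5 in the Protocol's. The SAP text names λ5 as the tested coefficient, but λ5 is clinician sex in its own equation. That is a separate labelling matter.

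**The concern.** A clinician random intercept describes how clinicians differ in their overall level. It cancels out of a Black-White difference taken within a clinician; variation between clinicians in that difference does not. The planned model sets this variation to zero and treats every encounter as independent information on the gap, although only about 40 randomised clinicians supply gaps.

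The Poisson assumption makes this worse, because there is no free residual variance to absorb what the model leaves out. The SAP also fits 1a separately in Black and White patients, which lets a clinician's effect differ by race. The Aim 2 model forces the two effects to move together and gives no reason.

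At stake is a confidence interval that is too narrow, and a chance grouping of small-gap clinicians in one arm being reported as a changed disparity. Disparity in objective communication is the primary outcome of Aim 2.

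**Working it through.** **Inputs from the documents.** 40 clinicians, 20 per arm; 240 post-period patients, 6 per clinician; 3 per race per clinician (racial-subgroup row of the SAP power table); mean 1.0; CV of the clinician's rate 0.2 to 0.5; two-sided 5%, 80% power.

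**Assumed.** τ, the SD across clinicians of the log Black/White rate ratio, and an exact 3+3 split at each clinician. The Protocol fixes only about 50% Black overall.

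**1. The plan's own figures reproduce.** The cluster-randomised formula for two Poisson rates is c = 1 + (1.96 + 0.84)²[(r0 + r1)/m + CV²(r0² + r1²)]/(r1 − r0)², with c = 20 per arm and r0 = 1. It gives r1 = 1.81, 1.92, 2.09 at m = 2 and 2.19, 2.30, 2.47 at m = 1, for CV 0.2, 0.35, 0.5. The SAP states 1.8, 1.9, 2.1 and 2.2, 2.3, 2.5. The 2b figures also reproduce using t with 38 df: 0.646, 0.659, 0.674 at m = 2 and 0.909 at m = 1. In both, the CV or ICC describes the clinician's level, not the gap.

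**2. Standard error of the interaction in 2a.** At mean 1 with 3+3 patients, a clinician's log gap has sampling variance 1/3 + 1/3 = 2/3. The true variance is 2/3 + τ²; the planned model uses 2/3. The ratio of model SE to true SE is √[(2/3)/(2/3 + τ²)], and type I error is 2Φ(−1.96 × ratio). At τ = 0.35: √(0.6667/0.7892) = 0.919, giving 7.2%. The last column gives rejection under the planned model at 1.96 in simulated null trials (400 to 2,500 per cell, mostly at CV 0.35).

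| τ | Middle 95% of clinicians' rate ratios, relative to the average, exp(±1.96τ) | SE ratio | Type I, formula | Type I, simulated |
|---|---|---|---|---|
| 0 | 1 | 1.00 | 5.0% | 3.6-5.1% |
| 0.2 | 0.68 to 1.48 | 0.97 | 5.7% | 4.7-6.0% |
| 0.35 | 0.50 to 2.0 | 0.92 | 7.2% | 6.5-8.6% |
| 0.5 | 0.38 to 2.7 | 0.85 | 9.5% | 9.0-10.9% |

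Changing only the reference distribution does not cure this: with t on 38 df the planned model still rejected in 6.6-6.9% at τ = 0.35 and 9.6-9.8% at 0.5.

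**3. What τ might be.** If the planned CV applies within each race, as the subgroup power rows assume, then τ² ≈ 2·CV²(1 − ρ), where ρ is the assumed correlation between a clinician's Black and White effects. With ρ = 0.5, τ equals the CV (0.2, 0.35, 0.5). With CV 0.5 and ρ = 0.75, τ = 0.35. This gives a scale, not an estimate.

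**4. Hypothesis 2b.** With residual variance s², the true gap variance is (2/3)(s² + 1.5τ²). In an intercept-only linear model the residual takes up 38/198 of the excess, so the model uses (2/3)(s² + 0.288τ²). With τ in outcome SDs and ICC 0.01 to 0.1, type I error is 5.1-5.2% at 0.1, 5.6% at 0.2, 6.3-6.4% at 0.3 and 8.4-8.7% at 0.5. Estimating the slope variance and using 38 df gives a simulated 4.9-5.2% at every τ.

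**5. Detectable effects with gap variation counted.** For 2a, exp[2.80 × √(2(2/3 + τ²)/20)] = 2.06, 2.11, 2.20, 2.34 at τ = 0, 0.2, 0.35, 0.5. For 2b at ICC 0.05, the detectable difference is 0.705 at τ = 0, 0.753 at 0.3 and 0.833 at 0.5. All lie within the SAP's stated ranges (1.8 to 2.5; 0.65 to 0.91), so this is mainly an error-rate problem in the analysis model.

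**6. The 2a test with slope and 38 df.** Null rejection was 3.4% at τ = 0, and 4.3% and about 6% in two sets of trials at 0.35. Rejection at a ratio of rate ratios of 2.0, planned test against amended test, was 83% to 80% and 87% to 83.5% at τ = 0, and 83% to 74% and 81% to 74.5% at τ = 0.35.

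**The case against.** The strongest reply is that the size rests on a number the documents do not contain. The CV of 0.2 to 0.5 is for the overall rate, and at τ of 0.2 or less the harm is negligible. That stands. A reader might infer that the Aim 2 test fails its 5% level outright; the documents do not support that, because the failure is conditional on gaps varying.

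A reader might also infer that the trial's rationale already says clinicians differ in bias. The Protocol's Background says only "This suggests that provider bias may contribute to disparities in communication and patient-centered care". A bias shared by all clinicians is the fixed Black term already in the model. Variation between clinicians is a reasonable inference, the more so because coaching is tailored to each clinician, but it is not stated.

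Nor do the 2a percentages carry over to 2b, where the residual absorbs part of the variance and the model is not written out.

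On practicality, the slope variance will often be estimated at zero: in simulated null trials, 66% of the time at τ = 0, 54% at 0.2 and 33% at 0.35. This calls for a pre-specified fallback but is no reason to omit the term. These fits used a fixed 3+3 layout and were not run in PROC GLIMMIX.

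**Conclusion.** The concern holds conditionally. For any gap SD above 0, the intercept-only 2a model understates the standard error of the race-by-arm term, and nothing else in either document corrects it. At mean 1.0, CV 0.35 and 3+3 patients, type I error is about 5-6% at SD 0.2, 7-9% at 0.35 and 9-11% at 0.5, against a nominal 5%. The 2b inflation is smaller, and its structure is an inference.

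The figures are for the SAP's post-period model. The argument carries over to the Protocol's version, because both of its intercepts also cancel from a within-clinician, within-period gap, but its error rate was not computed. Unequal race splits would change the figures, and a clinician with patients of one race contributes no within-clinician gap.

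A reader might take this to undermine the trial's main result. It does not: the Protocol and SAP name 1a as the primary hypothesis, and its arm effect is a clinician-level comparison for which the random intercept is the right term. The change is worth making because Aim 2 is a main aim and the remedy is small.

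**What to change.** - **2a, both documents:** add b1k(Black_i − 0.5), with b1k normal and independent of the clinician intercept (variance-components structure).
- **2b:** write out the linear model, with the same slope term.
- **Test:** refer the race-by-arm coefficient to clinician-level degrees of freedom, about 38 (40 clinicians minus 2 arms), recalculated for the clinicians who contribute both races.
- **Fallback:** state in advance that if the slope variance is estimated at zero, the model reverts to the random intercept with the same degrees of freedom.

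A small-sample-corrected robust standard error, or a comparison of clinician-level gaps on 38 df, would also address the point. One method should be named before the data are analysed.

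**Cost.** One model term and a few lines of text. At a ratio of rate ratios of 2.0, about 3 points of power are lost if gaps do not vary, and the test is then slightly conservative. At SD 0.35 the rejection rate falls by about 7 to 9 points, part of which is the planned test's inflated error rather than real power.
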